4.2.10 SUBJECTS WITH TWO SENSORS INSERTED

Subjects with two sensors inserted will be issued two transmitters to be worn over the sensors. Transmitters will be designated as primary (left arm) and secondary (right arm) and will have distinguishing visual marks to ensure matching to the correct limb. Each transmitter is linked to a specific sensor as described in the Eversense® 180 CGM system User Guide. Subjects will be issued a hand-held display which will be used for entering calibration information into the primary transmitter only. The secondary transmitter worn on the opposite arm will have the ability to collect and log data only and will not calculate and store glucose. The handheld device, when paired to the secondary transmitter, will only display battery level and the placement guide used for wearing the transmitter as described in the Eversense® 180 CGM system User Guide.

The secondary transmitter will use the SMBG calibration points collected and entered into the primary system (using the same time stamp information) for calculation of glucose results in the analysis data set.

This subset of subjects will be used to explore the following endpoints: PARD, and dominant vs non-dominant arm effects. Analysis of data from subjects with two sensors inserted is further described in Section 11. Additionally, this subset of subjects will continue participation for 365 days of sensor wear. At Day 180, the primary sensor will be removed and a new sensor will be inserted. The secondary sensor will remain in situ for observation of sensor life for up to 365 days.

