5.3 SENSOR REPLACEMENT

Primary sensors that fail within 30 days of sensor insertion will be replaced at an unscheduled visit. Subjects will continue to follow their originally scheduled visits.

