5.4 PRIMARY SENSOR BLINDING

During the study the primary system may go into a “blinded mode” (called Clinical Mode by the device). Under these circumstances subjects will continue to wear the system, and enter calibrations (as prompted) and SMBG values, but the system will not provide sensor glucose information or glucose related alerts. Subjects should continue with all remaining sensor accuracy visits with the blinded system.

If a primary sensor displays a “sensor replacement” alert, it (and the secondary sensor if applicable) will be removed at an unscheduled visit, and the subject will be withdrawn.

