7.3 SENSOR SITE

The sensor insertion sites will be assessed (visually, as well as by palpation, and by eliciting Subject history) at each clinic visit, and the Subject will be instructed to call the clinic if signs or symptoms of irritation or infection (increased temperature, pain, redness, warmth, swelling, or purulence) are observed at any time. Sensor site infections are to be treated with antibiotics, either topical or oral.

At any time during the study, if the study physician determines that there is an infection at the sensor insertion site that has not responded to treatment within 3 days, the sensor will be removed. In the event of an insertion site infection and sensor removal in a subject with one sensor only, the subject will be withdrawn from the study and not replaced. In Subjects with two sensors, if the primary sensor is removed due to infection, the other sensor will become the primary sensor.

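### Protocol 5.3 and 5.4 give opposite follow-up for a primary sensor that fails within 30 days and shows a replacement alert, and a replaced sensor is then analysed under visit labels that do not match its age

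*Protocol*

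**What the plan says.** Protocol 5.3 states: "Primary sensors that fail within 30 days of sensor insertion will be replaced at an unscheduled visit". It then adds: "Subjects will continue to follow their originally scheduled visits".

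Protocol 5.4 deals with a primary sensor that shows a sensor-replacement alert. In that case the primary, together with any secondary, "will be removed at an unscheduled visit, and the subject will be withdrawn". No day limit is attached, and 5.3 is not mentioned.

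Protocol 7.6.4, the list of reasons for withdrawal, does not include this alert. Protocol 11.1.3 says that end of sensor life closes the accuracy evaluation of that sensor; it does not say that the subject leaves the study.

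On the analysis side, SAP 6.1.3 assigns data to the nominal visit on the case report form. SAP 6.1.2 counts study days from sensor insertion, with Day 0 at Visit 2, and does not say which sensor counts after a replacement. Protocol 11.3.2.1 defines MARD through 180 days of sensor use, and 11.3.2.6 uses the by-visit table to show stability throughout sensor life.

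**The concern.** A primary sensor that stops working in its first 30 days and raises the replacement alert meets the conditions of both 5.3 and 5.4. One section keeps the subject in follow-up with a new sensor; the other removes every sensor and ends participation. With no order of precedence, two sites could handle the same event differently and both be following the protocol. That affects who contributes late accuracy data. Because subjects who leave are not replaced (7.6.6) and the sample size rests only on reaching 120 subjects at Day 180 (11.3.2.2), each withdrawal counts against the one sizing target.

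The second matter arises only if 5.3 is followed. The replacement sensor inherits the original visit labels, so the later rows of the by-visit table mix sensors of different ages. The table is meant to show how accuracy holds up as a sensor ages, and the mixing adds younger sensors to its late rows.

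**Working it through.** **The rules side by side**

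| | 5.3 | 5.4 | 7.3, two-sensor subjects |
|---|---|---|---|
| Trigger | Failure of the primary (not defined) | Replacement alert on the primary | Primary removed for site infection |
| Time limit | 30 days from insertion | None | None |
| Primary | Replaced | Removed | Removed |
| Secondary | Not mentioned | Removed | Becomes the primary |
| Subject | Continues, original visits | Withdrawn | Continues |

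5.3 and 5.4 overlap when three things hold: the sensor has failed, the alert is shown, and no more than 30 days have passed since insertion. Protocol 11.1.3 makes the overlap plausible: the transmitter checks for premature failure, and a sensor past the threshold stops giving readings. The documents do not define the alert, so the overlap is a natural reading rather than a certainty. 7.3 has a different trigger and is not part of the conflict.

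**Sensor age under 5.3**

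Age at visit = visit day − day of replacement.
- Replaced on Day 10: 60 − 10 = 50 days old at the Day 60 visit; 180 − 10 = 170 at the Day 180 visit.
- Replaced on Day 30: 60 − 30 = 30 days old at the Day 60 visit; 180 − 30 = 150 at the Day 180 visit.

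For a single replacement made by Day 30, the sensor in the Day 180 row is therefore up to 30 days younger than the label.

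**Pairs at stake (table in Protocol 11.1.4, based on 160 inserted)**

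1. Reproduce the total: 6,720 + 3,360 + 3,360 + 6,720 + 6,720 + 6,720 + 6,510 + 5,880 + 5,460 = 51,450. Adding 5,600 or 6,000 for Day 180 gives 57,050 or 57,450, as stated.
2. Pairs per subject per visit: 6,720/160 = 42, and the same at every visit before Day 180; at Day 180, 5,600/112 = 6,000/120 = 50.
3. Maximum forgone from Days 60 to 180 by one withdrawn subject: 4 × 42 + 50 = 218. Withdrawal before the Day 30 visit adds another 42 (260).
4. After the table's own attrition: (6,720 + 6,510 + 5,880 + 5,460 + 5,600)/160 = 30,170/160 = 188.6; with 6,000 at Day 180, 30,570/160 = 191.1.
5. Scale the total to the 180 insertions now planned: 57,050 × 180/160 = 64,181.
6. Assume 2 to 10 of 180 subjects are affected and all are withdrawn: 2 × 188.6 = 377, or 0.59%; 10 × 188.6 = 1,886, or 2.94%. The upper-end totals (191.1 pairs; 57,450 × 180/160 = 64,631) give 0.59% and 2.96%. Using the 218 maximum against 64,181 gives 0.7% to 3.4%.

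**What that could do to MARD**

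Leaving out a share f of pairs whose MARD differs by d points from the rest moves the overall figure by about f × d. At f = 2.9%, a move of 0.1 point needs d = 0.1/0.029, about 3.4 points. The documents give no basis for a value of d.

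**The case against.** The best defence is that failure and alert are different events, or that 5.3, being limited in time, is the exception to the general rule in 5.4. Either may be what the sponsor means, and device operation is referred to a User Guide that is not among these documents. But neither section says so, and 11.1.3 describes device-detected loss of function in terms of failure. What stands is that the overlap is narrow: it ends 30 days after insertion and requires the alert to count as a failure.

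It can also be said that sensor age is recoverable, since sensor identifiers are recorded (4.2.3, 10.2.2), and that analysis by nominal visit is an explicit choice. Both are true. They make the remedy cheap, but the planned table still does not show age.

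Three stronger readings are tempting and are not supported:
- A reader might infer that 5.3, 5.4 and 7.3 are three rules for the same loss. They are not: 7.3 says "In Subjects with two sensors, if the primary sensor is removed due to infection, the other sensor will become the primary sensor", and its trigger is infection only. It is enough to note that in two-sensor subjects the cause of primary-sensor loss decides whether the secondary is kept, and that no reason is given.
- A reader might set 5.4 against 4.2.10, which says "The secondary sensor will remain in situ for observation of sensor life for up to 365 days". That sentence follows the Day 180 exchange of the primary and describes the extension; it makes no promise about early loss of the primary. The secondary also depends on calibration points entered into the primary system, so ending both together is a coherent choice.
- A reader might infer that MARD is biased. Nothing in the documents shows that.

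Nor does the planning table settle which rule is meant. It keeps 160 of 160 subjects through Day 60, which fits 5.3 better than 5.4, but it allows for no early loss of any kind.

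**Conclusion.** The conflict between 5.3 and 5.4 is real but limited to the first 30 days after insertion and to alerts that count as failures. No text gives precedence, and 7.6.4 does not resolve it. The sensor-age mismatch under 5.3 is a separate and equally limited gap: a replaced sensor can be about 150 days old at the visit labelled Day 180.

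The size cannot be fixed from the documents, because they give no early-failure or alert rate. On the assumption of 2 to 10 affected subjects among 180, all withdrawn and otherwise following the table's attrition, about 0.6 to 2.9% of planned pairs turn on which rule a site applies. The study is descriptive and no effect on MARD is shown. The point is worth correcting because it decides who stays in follow-up and what the stability table describes, not because a result is known to be wrong.

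**What to change.** The sponsor should reconcile Protocol 5.3, 5.4 and 7.6.4 so that a replacement alert within 30 days of insertion has one stated outcome for the primary sensor, any secondary sensor and the subject, and should define failure in relation to the alert. This review does not say which outcome is right.

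In the SAP, define Study Day for the accuracy analyses from the insertion date of the sensor actually worn. Present the by-visit accuracy table (Protocol Table 8, SAP A.9) also by actual sensor age, or with replaced sensors shown separately.

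The cost is a protocol clarification, a short SAP edit and one extra table. No new data are needed, since sensor identifiers and insertion dates are already recorded.

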5.5 SPONSOR PRESENCE AT VISITS

One or more technical representatives of the sponsor may be present during clinic visits under supervision of the Clinical Investigator.

5.6 PHOTOGRAPH/VIDEOGRAPHY

The procedure for inserting or removing the sensors may be photographed and/or recorded on video after receiving subject authorization in writing. Only the area immediately nearby the sites will be photographed and/or recorded and subjects will not be identifiable.

At the discretion of the study Sponsor and primary investigator, at any visit, the locations of the devices may be documented for safety reasons through a variety of means including, but not limited to, photography, x-ray, and ultrasound examination.

6 CLINICAL LABORATORY EVALUATIONS AND ESTIMATED BLOOD VOLUMES

Standard clinical laboratory analysis equipment, procedures and quality control will be used for all laboratory evaluations in this clinical trial. Blood samples will be drawn for glycemic challenges and for laboratory measurement of HbA1c. Blood loss will not exceed the American Red Cross Guidelines of more than 475 ml over any 8-week period. Hematocrit will be assessed using local lab or Point of Care testing device.

7 SUBJECT SAFETY, STOPPING RULES, AND STUDY EXIT

7.1 DIABETES AND SAFETY CONSIDERATIONS DURING CLINIC VISITS

Diabetes care in the Clinic Visit will be the responsibility of the Investigator and appropriately delegated staff. As diabetes self-management is an integral part of diabetes care, the Investigator may work closely with the Study subject, when appropriate, to determine the best approach, however the ultimate responsibility lies with the Investigator.

7.2 MEDICAL OVERSIGHT

There will be staff trained in emergency response, and there will be an EKG and emergency cart available at the site at all times. Site-specific safety guidelines will be utilized for subject safety management during periods of hyperglycemia (including monitoring blood ketones) and hypoglycemia. Study staff (MD, DO, PA or NP who has experience in diabetes management) will also be immediately available at all times during hypoglycemia

and hyperglycemia challenges. A nurse, nurse practitioner, or physician/PA will be at the bedside or on the unit throughout the entire visit.

7.3 SENSOR SITE

The sensor insertion sites will be assessed (visually, as well as by palpation, and by eliciting Subject history) at each clinic visit, and the Subject will be instructed to call the clinic if signs or symptoms of irritation or infection (increased temperature, pain, redness, warmth, swelling, or purulence) are observed at any time. Sensor site infections are to be treated with antibiotics, either topical or oral.

At any time during the study, if the study physician determines that there is an infection at the sensor insertion site that has not responded to treatment within 3 days, the sensor will be removed. In the event of an insertion site infection and sensor removal in a subject with one sensor only, the subject will be withdrawn from the study and not replaced. In Subjects with two sensors, if the primary sensor is removed due to infection, the other sensor will become the primary sensor.

7.4 OTHER CONSIDERATIONS AND SAFETY ASSESSMENTS

- An assessment and documentation of adverse events occurring in clinic and during home use will be on-going.
- Urine pregnancy testing (for women of childbearing potential) will be performed at the start of visits as scheduled with study exit as described in section 7.6.5 if the Subject is pregnant.
- Subjects will arrive at Clinic Visits, having followed their usual diabetes care, including insulin dosing and food.
- Subjects must not be febrile in the 24 hours prior to Clinic Visits 2-15.
- IV access is required during most clinic visits. In the event of loss of IV access, glucose measurements may be made using Subject SMBG meter or alternate sampling method for subject care. Investigator may determine when further attempts at IV access will cease.
- In order to prevent adverse effects that may occur as a result of the hyperglycemia challenge, unlimited sugar free oral fluids should be provided to subjects to prevent dehydration secondary to hyperglycemia.

7.5 HYPOGLYCEMIA

The Subject will be asked to alert the study team anytime he or she experiences symptoms of hypoglycemia (i.e., shakiness, dizziness, sweating, headache, moodiness,

difficulty concentrating, or the Subject's usual symptoms of hypoglycemia). The symptoms will be confirmed by Subject SMBG Meter and/or YSI. Intravenous access is to be maintained during the Clinic Visit and available for hypoglycemia treatment as indicated. Glucagon by injection and IV dextrose will be available at the site and may be used as clinically indicated. A heating pad or heating chamber may be used during the session to minimize potential for occlusion or to enable the insertion of the IV.

7.5.1 GUIDELINES FOR TREATMENT FOR HYPOGLYCEMIA WHEN NOT IN A CHALLENGE PERIOD

Subject safety prevails, and Investigator may treat for hypoglycemia when clinically indicated at any time. However, when the subject is not in a challenge and becomes hypoglycemic and safety is a concern, the guidelines below should be followed to treat the hypoglycemia.

Glucose level	Glucose administration	Safety
<60 mg/dL	Treat hypoglycemia as appropriate using oral carbohydrates such as glucose tablets (~15 g. and check glucose in 15 minutes minimum, repeat) until BG >60 mg/dL	
60 – 75 mg/dL	Treat hypoglycemia as appropriate using oral carbohydrates such as glucose tablets (~10 g. and check glucose in 15 minutes minimum, repeat) until BG >75 mg/dL	If subject is unable to ingest glucose orally, IV dextrose (~2-3 mL/kg D10 intravenous or up to 30 ml D50%) may be used. Glucagon will be available for emergency.

- Risk for severe hypoglycemia is defined as any of the following situations:
 - Glucose <50 mg/dL
 - The subject is unable to cooperate with oral treatment of hypoglycemia
 - The glucose is dropping at a rate that may not respond adequately to oral treatment
 - The subject experiences symptoms of neuroglycopenia (e.g. lethargy, disorientation, confusion [disordered processing of information or communication], or inappropriate behavior)

- The subject experiences symptoms of severe hypoglycemia (i.e. hypoglycemic seizure or loss of consciousness)
- In the event that there is NO intravenous access and the subject is at risk for severe hypoglycemia (as defined above), the subject will be treated with 1 mg of glucagon subcutaneously or intramuscularly.
 - The drug will be reconstituted and administered per package insert/instructions.
 - Glucagon may be repeated as needed every 20 minutes to achieve glucose level ≥ 75 mg/dL. Once the subject is able to consume oral treatment, the subject will be treated orally with fast acting carbohydrate as needed until a glucose level of ≥ 75 mg/dL is achieved. Orange juice and milk will be avoided after glucagon administration.
 - Attempts will be made to reestablish intravenous access.
- The accuracy visit will be stopped if the subject experiences a hypoglycemic seizure or loss of consciousness and only safety procedures will be continued. The study physician/PA or nurse practitioner will take control over glucose sampling decisions in order to stabilize the subject's glucose between 100-300 mg/dL and determine the appropriate subject disposition (i.e. home or medical facility).

7.5.2 HYPERGLYCEMIA AND BLOOD KETONE MONITORING

The Subject will be asked to alert the study team anytime he or she notes symptoms of hyperglycemia (i.e. thirst, increased urination, or other symptoms). A glucose level will be confirmed by YSI or Subject SMBG meter.

Fingerstick blood ketones, using a commercially available ketone meter, will be monitored if blood glucose ≥ 300 mg/dL hourly until resolved. If glucose >400 mg/dL and no symptoms and no ketones, the cause of the hyperglycemia will be investigated and treated as appropriate by the Investigator.

If blood ketones > 1.5 mmol/L; subject participation in glucose challenges will be stopped for the day (see below). Appropriate care will be provided, including fluids and insulin as determined by Investigator. Standard-of-care troubleshooting for insulin pump users will take place, including change of infusion set if indicated and insulin by injection if indicated. If the subject's home parameters are not felt to be working adequately due to hyperglycemia, ketonemia, or other factors (e.g. intercurrent illness), the study MD

or NP will administer corrective insulin either via insulin syringe or via a new pump site using an ISF determined to be appropriate for the setting and a goal glucose of 120 mg/dL. The subject will continue to be monitored until a glucose level between 100-300 mg/dL and ketone measurement <0.6 mmol/L has been achieved (or the subject is discharged to an appropriate medical team).

7.5.3 GUIDELINES FOR TREATMENT OF HYPERGLYCEMIA AND KETONES WHEN NOT IN A CHALLENGE

Subject safety prevails, and Investigator may treat for hyperglycemia when clinically indicated at any time. However, when the subject is not in a challenge and becomes hyperglycemic and safety is a concern, the guidelines below should be followed to treat the hyperglycemia.

Ketone				
BG		<0.6	0.6-1.5	>1.5
	<300	
 Ketone testing will be repeated hourly until <0.6 Subject will be treated with SQ or IV insulin targeting 120mg/dL using subject's insulin sensitivity factor 	
 Glucose challenges will be stopped, and subject will enter free range glucose control Ketone testing will be repeated hourly until <0.6 Subject will be treated with SQ or IV insulin targeting 120mg/dL using subject's insulin sensitivity factor 	
>300		
 Ketone testing will be repeated hourly until BG <300 	
 Ketone testing will be repeated hourly until <0.6 Subject will be treated with SQ or IV insulin targeting 120mg/dL using subject's insulin sensitivity factor Continue monitoring until BG <300 	
 Glucose challenges will be stopped, and subject will enter free range glucose control Ketone testing will be repeated hourly until <0.6 Subject will be treated with SQ or IV insulin targeting 120mg/dL using subject's insulin sensitivity factor Continue monitoring until BG <300

- Insulin treatment for hyperglycemia or ketones should be done using the subject's own insulin. In the event that the subject's own insulin appears to be compromised (not having the expected effect on the subject's blood glucose), appropriate insulin (based on the subject's normal insulin type and concentration) provided by the site may be used.

7.6 SUBJECT STOPPING RULES

7.6.1 STOPPING CHALLENGES – REATTEMPT IN FUTURE GLUCOSE CHALLENGES

Glucose challenges will be stopped, and subject will enter free range glucose control if:

- Subject requests to end the challenge due to discomfort (desires food and/or insulin)
- Subject ketone measurement >1.5 mmol/L

These subjects will be eligible to continue participating in challenges at future accuracy visits. Blood sample collecting and analysis on YSI will continue during this time.

7.6.2 STOPPING CHALLENGES – NO RE-ATTEMPT IN FUTURE GLUCOSE CHALLENGES

- Subject develops significant nausea, vomiting, abdominal pain, chest pain, or develops ketoacidosis
- The subject is unable to cooperate with oral treatment of hypoglycemia
- The glucose is dropping at a rate that may not respond adequately to oral treatment, and the administration of glucagon is required
- The subject experiences symptoms of neuroglycopenia (e.g. lethargy, disorientation, confusion [disordered processing of information or communication], or inappropriate behavior)

7.6.3 STOPPING ACCURACY VISIT

During accuracy visits, study procedures other than those required for subject safety will be stopped for that day if any of the following occur:

- The subject had a serious adverse event that is deemed either related to study or in the investigator's opinion requires stopping
- Medical intervention is required to treat severe hypoglycemia (seizure, unconsciousness, etc.)
- Adequate intravenous access cannot be maintained
- The YSI and back-up YSI, (if available), stop functioning and neither can be re-established within 2 hours.
- Subject requests to stop
- Investigator determines it is in Subject's best interest to stop the accuracy visit

- Subject develops DKA

